8.4 Follow-up

After study termination, there are no scheduled examinations although the following information should be sent annually to the study management in Muenster:

- **Status:** patient is dead, alive with recurrence, alive without recurrence or lost to follow-up (indicate the day of last contact)
- In **case of dead**, the date and cause of death should be noted.

The study management in Muenster will contact the respective treating oncologist in case that no information on follow-up is provided.

9 Management and reporting of adverse events/adverse reactions

9.1 Definitions

Adverse reactions (AR), acute toxicity: the **Common Terminology Criteria for Adverse Events (CTCAE)**, formerly called the Common Toxicity Criteria, are a set of criteria for the standardized classification of adverse reactions or effects of medical treatment used in cancer therapy. The CTCAE system is a product of the US National Cancer Institute (NCI).
ISRT 20 Gy in localized indolent GI-NHL, Study protocol, version 01, 23.08.2020 Page 27 of 75

The clinical relevant version 3.0 was released in 2006 (see Appendix 16.5). It uses a range of grades from 1 to 5, specific conditions and symptoms have values or descriptive comment for each level, the general guideline is:

Grade 1	mild
Grade 2	moderate
Grade 3	severe
Grade 4	life-threatening
Grade 5	death

Adverse reactions (AR), chronic toxicity: the **LENT SOMA** (Late Effects on Normal Tissue, Subjectiv, Objectiv, Management) score criteria are a set of criteria for the standardized classification of adverse effects of medical treatment used in cancer therapy. The LENT SOMA Tables for the gastrointestinal system with regard to the stomach and the small intestine are:

Grade 1/ 2/ 3/ 4. **S**ubjective, **O**bjective, **M**anagement, **A**lytic (see Appendix 16.6).

An **Adverse Event (AE)** is defined as an event impairing the patient's health status in comparison to the status before therapy regardless if this event is related to RT or not. Pre-existing medical conditions, planned hospitalizations, study diagnostic testing and procedures as well as an asymptomatic lymphocytosis are not considered as AE. Adverse events categorized as "serious" (SAE) are for e.g. results in death, illness requiring hospitalization, events deemed life-threatening, results in persistent or significant disability/incapacity, a congenital anomaly/birth defect or medically important condition. The grades of adverse events are defined as:

Grade 1	Mild; asymptomatic or mild symptoms; clinical or diagnostic observations only; intervention not indicated.
Grade 2	Moderate; minimal, local or noninvasive intervention indicated; limiting age-appropriate instrumental activity living
Grade 3	Severe or medically significant but not immediately life-threatening; hospitalization or prolongation of hospitalization indicated; disabling; limiting self care activity of daily living
Grade 4	Life-threatening consequences; urgent intervention indicated.
Grade 5	Death related to AE

9.2 Collection and reporting of AE/AR

Events linked to tumor progression are not considered to be severe AE or AR.

Collection/reporting of AR:

Occurrence and grading of AR are to be documented on the forms on acute and chronic toxicity during the follow-up and sent to the study center within 7 days. If the respective AR is not mentioned on the RT-form, number (see Appendices 16.5 for AR-CTCAE and 16.6 for AR-LENT SOMA) and grading should be added by signature. If an AR is not listed in CTC-criteria or the LENT SOMA-criteria, the category "Other" is applied and staged according to grading of AR (s. chapter 9.1).

In case of an AR causing hospitalization, prolongation of a hospitalization, physical handicap, life threatening events or gametopathy, the duration and therapy of AR as well as the possible causal link to lymphoma or therapy are to be documented on the form for acute or chronic AR (AR-CTCAE or AR-LENT SOMA) and sent to the study center within 24 h during RT and within 15 days during follow-up (per [contact]). Severe AR are carefully reviewed by the study center in Muenster and evaluated, according to their causal relation to the study treatment.

An accumulation of **grade 3 or grade 4 adverse reactions** according to CTCAE or LENT SOMA, in comparison to the prospective Muenster trials GIT NHL 01/92, GIT NHL 02/96 or DSGL may require a preliminary end of study (see 9.2.3).

Collection/reporting of AE:

Occurrence and grading of AE are to be documented on the RT-form during the follow-up and sent to the study center within 7 days. If the respective AE is not mentioned on the RT-form, the symptom with number (see Appendices 16.5 and 16.6 for AR/AE) and grading should be added by signature.

In case of an AE causing hospitalization, prolongation of a hospitalization, physical handicap, life threatening events or gametopathy, the duration and therapy of AE as well as the possible causal link to lymphoma or therapy should be documented as SAE and sent to the study center within 24 h during RT and within 15 days during follow-up (per [contact]). SAE are carefully reviewed by the study center in Muenster and evaluated, according to their causal relation to the study treatment.

There is no statutory reporting obligation for serious adverse events SAE in this study.

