2.1 Background Information and Rationale

Primary gastrointestinal lymphomas are rare tumors with an incidence of 0.1-1/100,000 per year. Extranodal indolent lymphomas comprise different histologic subtypes e.g. as marginal zone lymphoma (MZL) or follicular lymphoma (FL). Extranodal MZL most frequently (66%) are located in the gastrointestinal tract, and involvement of the stomach accounts for 30%. Gastrointestinal MZL show low cause-specific mortality rates, they are less likely to relapse than non-gastrointestinal extranodal MZL. MZL often arise multifocally within the stomach. Bowel cases of gastrointestinal FL are most common (63%), followed by gastric cases (18%). Bowel cases of FL have better outcomes (5-year OS = 81%, $p < 0.001$) in comparison to gastric FL cases (5-year OS = 53%). Gastrointestinal lymphomas (GIL) represent a low risk of distant dissemination.

Actual guidelines on gastrointestinal indolent lymphoma favour an organ-preserving approach. The standard treatment of *Helicobacter pylori* (HP) positive gastric lymphoma is an antimicrobial therapy. In case of persisting lymphoma after HP eradication and in case of HP-negative lymphoma patients are treated with local radiation therapy with curative intent. For indolent lymphoma of the bowel surgical treatment is limited to rare complications (perforation or bleeding). Depending on the primary localization and extent of the disease uncomplicated indolent lymphomas of the bowel are treated with local (NHL confined to duodenum) or locoregional "whole abdominal" (NHL of the small bowel or duodenal lymphoma with confirmed/ suspected involvement of small bowel) radiation therapy.

For extranodal indolent Non Hodgkin lymphoma regardless of the localization the radiation dose range is currently reported between 20 and 30 Gy (Lowry 2011). The actual guidelines of the International Lymphoma Radiation Oncology Group (ILROG) for radiation dose given to extranodal indolent non Hodgkin lymphoma (NHL) by Involved Site Radiotherapy (ISRT) are 24-30 Gy depending on the diseased organ, for gastric and duodenal lymphoma 30 Gy are recommended (Yahalom 2015).

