9.2.1 Relationship of AR/AE to study treatment

The causal relationship between an AE, especially SAE, or an AR and the study treatment will be evaluated by the lead investigators and the study center in Muenster.

Definitely related:	The AE/AR shows a substantial temporal and causal relationship to RT making other possibilities unlikely.
Probable:	The temporal and causal relationship between RT and the AE/AR is reasonable assumed but alternative explanations or causalities are not definitely ruled out.
Possible:	A temporal sequential relationship between AE/AR and RT is suggested but the clinical pattern of AE/AR is not typical .
Unlikely:	The relationship between RT and the occurred AE/AR is improbable and other medical conditions , therapies, diseases, medication or a lymphoma progression may better explain the AE/AR.
Not related:	The AE/AR shows no known chronological order or temporal relationship to RT and is most likely caused by another etiology .
Not assessable:	The available data does not permit to evaluate the relationship between AE/AR and study treatment.

In any case, the outcome of AE/AR whether causal relationship to treatment exists or not, has to be reported according to the following scheme.

Recovered/ Resolved:	Complete restoration of clinical state before AE/AR
Recovering/ Resolved:	Reduction in intensity of symptoms/signs already occurred suggesting a complete recovery during the further investigation
Not recovered/ Not resolved	Clinical condition of patient remains unchanged or worsened
Recovered resolved with sequel:	Incomplete resolving or resolution of AE/AR with persistent after-effects which should be graded
Fatal:	AE/AR leading to death (grade V toxicity, SAE, s. 9.2.3).
Unknown:	Incomplete or inconsistent information on outcome

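### The opening sentence of section 9.2 on progression-linked events contradicts the AE/SAE rules in 9.1, 9.2 and 9.2.1, so whether a serious event is counted depends on an undefined attribution

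*Protocol*

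**What the plan says.** The rule at issue is the first sentence of Protocol section 9.2: "Events linked to tumor progression are not considered to be severe AE or AR". The section does not say what makes an event linked to progression, on what evidence, or who decides.

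Other parts of the protocol bear on the same events:

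- **9.1** defines an AE as an impairment of health compared with the status before therapy, "regardless if this event is related to RT or not". It then lists what is not an AE (pre-existing conditions, planned hospitalizations, "study diagnostic testing and procedures as well as an asymptomatic lymphocytosis are not considered as AE"). Progression is not on that list. Seriousness is defined by outcome, such as death, hospitalization or threat to life.
- **9.2, further down**, says that for an AE with such an outcome "the duration and therapy of AE as well as the possible causal link to lymphoma or therapy should be documented as SAE". It adds that "SAE are carefully reviewed by the study center in Muenster and evaluated, according to their causal relation to the study treatment".
- **9.2.1** covers any AE, SAEs in particular, and any AR. Their causal relation to treatment "will be evaluated by the lead investigators and the study center in Muenster". The category *Unlikely* includes the case where "medication or a lymphoma progression may better explain the AE/AR".
- **3.2.2** makes the incidence of AEs and SAEs a secondary endpoint.

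**The concern.** A site with a patient hospitalized for a bleed that may come from progressing lymphoma gets two answers. The opening sentence of 9.2 suggests that the event is not to be classed as severe. The SAE rule a few paragraphs later says to document it as an SAE, possible lymphoma link included. The protocol does not say which prevails.

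Attribution can be difficult here. Section 2.1 says that for indolent bowel lymphoma "surgical treatment is limited to rare complications (perforation or bleeding"), so it treats these events as possible complications of the disease. Appendix E grades gastrointestinal hemorrhage and perforation as toxicity, and the stomach table in Appendix F grades hematemesis, melena and perforation. One clinical event can thus be read as disease or as radiation injury.

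Two things are at stake. SAE incidence can come out too low, because an exclusion can only remove events. And a radiation injury labelled as progression may escape the review of severe reactions, in an open-label trial whose primary objective (3.1.1) names safety alongside efficacy.

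**Working it through.** The protocol gives no figure for this point, so the check is mainly a comparison of texts.

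**Step 1. Does the rule conflict with the definitions?** Under 9.1 the cause of an event is irrelevant to AE status, seriousness depends on outcome, and progression is not an exclusion. A progression-related hospitalization is therefore an AE and meets a seriousness criterion. The opening sentence of 9.2 makes the classification depend on cause. The two conflict.

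**Step 2. Does it conflict with its own section?** The SAE rule in 9.2 asks for the possible link to lymphoma to be recorded on the SAE report. That instruction presupposes that events possibly due to lymphoma are reported as SAEs.

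**Step 3. Does it conflict with the causality scheme?** In 9.2.1, progression as the better explanation is an outcome of central assessment, recorded as *Unlikely*. The category would have little use if such events were not submitted. Appendix E points the same way, more weakly: it lists disease progression among the grade 5 death terms, but it reproduces a general grading table.

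**Step 4. Does the word *severe*, rather than *serious*, remove the conflict?** There are two readings.

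- *Read as serious:* the sentence takes events out of SAE incidence, the endpoint in 3.2.2.
- *Read as a grade:* 9.1 labels grade 3 as severe. The sentence then affects grade 3 reactions, whose accumulation with grade 4 may end the study under 9.2, and toxicities of grade III or higher under 9.2.3.2.

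The protocol does not keep the words apart. Section 9.2 describes AR causing hospitalization or threat to life and then calls the reactions reviewed by the study center severe. Section 9.3 also uses severe loosely for adverse events. Either reading touches an endpoint, a review step or a stopping reason.

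**Step 5. What is counted elsewhere?** Progressive disease is a response category of the primary endpoint (3.2.1). EFS, PFS, RFS, LSS and OS (3.2.2) capture failure, progression, recurrence or death. Non-response and rapid relapse are stopping reasons (9.2.3.2). These record that control was lost or that the patient died. They do not record a non-fatal bleed, perforation or hospitalization as a safety event.

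**Step 6. Size.** The only firm arithmetic is the weight of one event. With the 83 patients to be assigned (11.2), 1/83 = 0.012, or 1.2 percentage points. With the 79 to be analyzed, 1/79 = 0.0127, or 1.3 points. The number of events affected would need the rate of serious progression-linked events, which the protocol does not give.

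**The case against.** The strongest reply is that this is a drafting slip with little consequence. The sentence removes nothing from the AE category. The SAE rule in the same section still captures serious events, and all AEs and ARs go to central causality assessment. AE and AR occurrence and grading must reach the study center within 7 days. Endoscopy with biopsies at 3, 6, 12 and 24 months, and CT at 6, 12 and 24 months, give evidence beyond a site's opinion. SAE incidence has no threshold or comparator, and all non-primary analyses are exploratory (11.3). Treating progression as efficacy and not as safety can also be deliberate.

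Much of this stands, and it rules out four stronger readings that a reader might infer:

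- *That sites remove these events before central review.* No text sets such a sequence, and the only attribution role that the protocol assigns is central. The gap is that 9.2 does not apply that role to its opening sentence.
- *That such events cannot appear in the SAE rate.* The SAE rule in 9.2 points the other way. They may be omitted; they are not certain to be.
- *That the main risk of the lower dose is concealed.* Loss of control is counted in the outcomes listed in step 5.
- *That the number of missing SAEs can be estimated from expected non-responders.* At response rates of 95% and 85%, 83 patients give 83 × 0.05 = 4.2 and 83 × 0.15 = 12.5 non-responders. The protocol gives no share of these with a serious lymphoma-linked event. Non-responders also include patients with no change, who have not progressed, and 2.1 calls perforation and bleeding rare, for bowel lymphoma.

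The reply does not remove the contradiction. Scheduled endoscopy and CT inform a judgement but do not say who makes it. A rule that can be followed in two ways makes an endpoint depend on the person applying it, exploratory or not.

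**Conclusion.** The contradiction is real and should be corrected. The opening sentence of 9.2 cannot be applied together with 9.1, the SAE rule in 9.2 and the scheme in 9.2.1, and the severe/serious wording does not reconcile them. As written, a serious bleed, perforation or hospitalization may or may not be counted, depending on who calls it progression-linked. The effect on SAE incidence, where there is one, is downward, by 1.2 percentage points per omitted event if all 83 planned patients form the denominator. How many events are affected is unknown. The primary test is untouched, and failure of lymphoma control remains visible in the efficacy outcomes and stopping reasons. The conclusion rests on the protocol text alone; separate reporting instructions, if they exist, could already settle the practice but were not available.

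**What to change.** Replace the opening sentence of 9.2 with a rule containing four elements:

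1. Any event meeting the 9.1 seriousness criteria is reported as an SAE even if progression is suspected. The lead investigators and study center assign its relation under 9.2.1.
2. Progression without any other seriousness criterion remains an efficacy event only.
3. *Serious* is used for the outcome criteria and *severe* for the grade, consistently, including in the AR paragraph of 9.2 and in 9.3.
4. SAE incidence is shown with and without events centrally rated as due to progression.

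The cost is a few extra SAE forms and one table row, using the review body already in place. The small downside is that some events appear under both efficacy and safety, which the two-way presentation makes visible.

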3.1.2 Secondary Objectives

The secondary objectives are the recording and analysis of the following criteria: quality of life and survival rates (event-free survival, lymphoma specific survival, progression-free survival, overall survival). During and after radiation treatment the acute and chronic adverse effects, including possible Adverse Events (AEs) and Serious Adverse Events (SAEs) will be collected.

Certain inflammatory cytokines are known to be elevated in patients with low-grade gastrointestinal lymphoma. In addition, cytokine profiles after radiation exposure are dose dependent. The effects of the radiation dose regimen on the production of cytokines (IL-1 β , IL-4, IL-8, TNF α) and other inflammation relevant molecules (Syndecan1, MMP-2 and S100 proteins) are to be investigated. Determination of the relationship between radiation exposure, inflammatory response and (complete) remission rate of each gastrointestinal lymphoma subtype is intended in order to optimize and personalize radiation therapy treatment for each patient.

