3.2.2 Secondary Endpoints

-**Quality of life** (QoL) according to EORTC (QLQ C30 and STO22), at baseline visit/ after 20 Gy (=last day of RT)/ 6 months after end of RT.

-**EFS**=Event-free survival (time from beginning of RT to any failure or death from any cause, all patients). Follow-up over 2 years after end of RT.

-**PFS**=Progression-free survival (time from beginning of RT to progression of lymphoma or death from any cause, patients in PR or SD). Follow-up over 2 years after end of RT.

-**RFS**=Recurrence-free survival (time from beginning of RT to recurrence of lymphoma or death from any cause, patients in CR). Follow-up over 2 years after end of RT.

-**LSS**=Lymphoma-specific survival (time from beginning of RT to death related to lymphoma or associated with the treatment, all patients). Follow-up over 2 years after end of RT.

-**OS**=Overall survival (time from beginning of RT to death from any cause, all patients). Follow-up over 2 years after end of RT.

-Level of **cytokines IL-1 β , IL-4, IL-8, TNF α** and other inflammation relevant molecules: **Syndecan1 and MMP-2** and **S100 proteins** at baseline visit/ after 4 Gy/ after 10 Gy/ after 20 Gy on last day of RT/ at 3 and 6 months after end of RT.

-**Acute toxicities** during treatment, 6 weeks after end of RT, according to NCI-CTC

-**Chronic toxicities** from 3 months up to 2 years after end of RT, according to NCI-CTC/ LENT-SOMA.

-Incidence of **Adverse Events** (AEs) and **Serious Adverse Events** (SAEs), continuously.

4 Study Design

-Single-arm, prospective, open label, interventional, multicenter study.

-Historic data from irradiated patients with indolent gastrointestinal lymphomas serves as a basis for the intended response rate.

-Participation of further international sites with expertise in radiation treatment of gastrointestinal lymphomas after approval of their Ethics Committee/ IRB.

-Number of 79 patients need to be analyzed.

-Justification for 'single-arm design' and for 'non-inferiority limit': the low prevalence of the disease, the limited risk of the study design (because of the option of renewed RT in case of persisting disease) and the benefit in terms of lower risk of adverse reactions due to the lower RT dose of 20 Gy in comparison to standard dose of 30 Gy.

5 Study Sites and Study Population

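### Sections 9.1 and 9.2 conflict on whether a serious radiation reaction is recorded as an SAE, so the SAE-incidence endpoint can vary by site and be understated for treatment-related events

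*Protocol*

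**What the plan says.** Section 9.1 defines an AE as an event that worsens the patient's health compared with the status before therapy, "regardless if this event is related to RT or not". SAEs are the AEs that are serious, and radiation-related events are not carved out.

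Section 9.2 then gives two collection paragraphs with the same triggers (hospitalization, prolonged hospitalization, handicap, threat to life, gametopathy):

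- **AR paragraph.** Duration, therapy and possible causal link "are to be documented on the form for acute or chronic AR (AR-CTCAE or AR-LENT SOMA") and go to the study center. The term SAE does not occur in this paragraph.
- **AE paragraph.** The same items "should be documented as SAE and sent to the study center within 24 h during RT".

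Section 9.2.1 labels a fatal AE or AR as an SAE. It gives no such label to a non-fatal serious AR.

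Section 3.2.2 makes this a secondary endpoint: "Incidence of Adverse Events (AEs) and Serious Adverse Events (SAEs), continuously". It lists acute and chronic toxicities as separate endpoints. The synopsis names AE and SAE monitoring as the assessment of safety, and 3.1.1 puts safety into the primary objective.

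**The concern.** The same clinical event can produce different SAE records depending on which section a site follows. The AR paragraph of 9.2 is specific, complete and has its own deadlines, so a site that applies it to an admission for radiation gastritis has complied without creating an SAE record. A site that starts from 9.1 files an SAE as well.

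Other parts of the protocol encourage the first reading by treating AR and AE as separate streams. The visit schedule in section 8 has separate rows for acute reactions, chronic reactions and adverse events. Section 9.2.1 names AE, SAE and AR side by side. Section 3.2.2 keeps toxicity and AE/SAE incidence apart.

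At stake is the SAE rate reported for 20 Gy. The events that can drop out are those attributed to radiation, so where they are lost the error favors the intervention. The trial is multicenter and international, so handling may well differ between sites.

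**Working it through.** **Step 1. The two paragraphs of 9.2 side by side.**

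| | Serious AR | Serious AE |
|---|---|---|
| Triggers | five listed criteria | the same five |
| Content | duration, therapy, causal link | the same |
| Deadline | 24 h during RT, 15 days in follow-up | the same |
| Recipient and reviewer | study center | study center |
| Where recorded | acute or chronic AR form | as SAE |
| Called an SAE | no | yes |

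Only the last two rows differ, and they decide the SAE count.

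**Step 2. Two events passed through the rules.**

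| Event | AR paragraph alone | 9.1 with both paragraphs of 9.2 |
|---|---|---|
| Admission for radiation gastritis | AR form only, SAE count 0 | AR form and SAE record, SAE count 1 |
| Admission for hip fracture (unrelated) | not an AR, so the AE paragraph applies: SAE count 1 | SAE count 1 |

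Under dual filing, the SAE records taken alone give the right count. If they are pooled with the AR forms to recover events from other sites, a dually filed event appears twice in an event count unless the records are linked. A count of patients with at least one event is not affected by duplicates.

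**Step 3. Bounds.** Let *r* be the proportion of patients with a non-fatal serious AR, *u* the proportion with another SAE (independent of the first), and *f* the fraction of serious-AR patients filed on the AR form only.

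- True any-SAE incidence = 1 − (1 − r)(1 − u)
- Patients missing from the count = 83 × f × r × (1 − u)

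The 83 is the number assigned to the trial (11.2), taken here as all treated. The protocol gives no value for *r*, *u* or *f*. With f = 0 nothing is missing. With f = 1 the loss is at its maximum, shown here for assumed rates of 2 to 10%:

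| u | r | True incidence (patients) | SAE route only (patients) | Patients missing | Relative understatement |
|---|---|---|---|---|---|
| 2% | 2% | 4.0% (3.3) | 2% (1.7) | 1.6 | 49% |
| 2% | 5% | 6.9% (5.7) | 2% (1.7) | 4.1 | 71% |
| 2% | 10% | 11.8% (9.8) | 2% (1.7) | 8.1 | 83% |
| 10% | 2% | 11.8% (9.8) | 10% (8.3) | 1.5 | 15% |
| 10% | 5% | 14.5% (12.0) | 10% (8.3) | 3.7 | 31% |
| 10% | 10% | 19.0% (15.8) | 10% (8.3) | 7.5 | 47% |

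Example, u = 10% and r = 5%: 1 − 0.95 × 0.90 = 0.145; 83 × 0.05 × 0.90 = 3.7; 1 − 0.10/0.145 = 0.31. The number missing scales with *f*: at f = 0.5 that row loses 1.9 patients. These are worst-case illustrations, not estimates.

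**The case against.** A reader might infer that the SAE endpoint, as the protocol defines it, excludes serious events caused by 20 Gy. The documents do not support that. The AE definition in 9.1 covers related events. The AE paragraph of 9.2 asks for the possible causal link to therapy on every SAE, and SAEs are then evaluated for their relation to treatment. The scale in 9.2.1 runs up to definitely related. Section 3.1.2 places AEs and SAEs within the effects of radiation: "the acute and chronic adverse effects, including possible Adverse Events (AEs) and Serious Adverse Events (SAEs) will be collected". Nothing says that the AR form replaces the SAE record. This part of the objection stands in full.

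It is also true that the events are not lost to the trial. Serious AR reach the same center by the same deadlines, and they appear under the acute and chronic toxicity endpoints. The termination criteria in 9.2 and 9.2.3.2 refer to toxicity grades, not to the SAE count. Analyses beyond the primary one are exploratory (11.3), so no confirmatory test depends on this count.

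Finally, how events are counted across forms could be set in a statistical analysis plan that is not shown. This answers only part of the point. Whether a site records an event as an SAE is a collection rule, and 9.2 sets it. An analysis plan can recover serious events from the AR forms only if those forms show seriousness, and 9.2 does not ask for the criterion met. Grade is not a substitute: Appendix E lists hospitalization for observation under grade 2 pneumothorax, and the LENT SOMA stomach table does not refer to hospitalization. The case report forms are not shown, so they may already capture this.

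**Conclusion.** The point holds as a conflict between 9.1 and 9.2, not as a definitional exclusion. By 9.1 a serious radiation reaction is an SAE; the AR paragraph of 9.2 lets a site record it without saying so. SAE incidence can therefore differ by site and be understated for treatment-related events, and dual filing has no linking rule.

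The size cannot be determined from the protocol. It lies between zero (all sites file on both routes) and all non-fatal serious AR (none do). Treating the upper bound as the expected effect would assume that every site reads the two routes as mutually exclusive, which the AE definition does not support. Fatal reactions are outside the problem because 9.2.1 already labels them SAEs. Safety oversight and the toxicity endpoints are not impaired. The count affected is nevertheless a stated secondary endpoint, so the two sections should be reconciled.

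**What to change.** 1. In the AR paragraph of 9.2, state that an AR meeting the seriousness list is also documented as an SAE, linked to its AR form by an event number and counted once.
2. In 3.2.2, define SAE incidence as the proportion of patients with at least one serious event from either the SAE records or the AR forms, each event counted once, reported overall and by relationship to RT.
3. If the AR forms do not already show seriousness, add a yes/no field. Where sites have already filed serious AR on the AR form only, this also allows them to be identified.

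The cost is two sentences and possibly one form field, with no new visits or procedures. The stated SAE rate may be slightly less favorable.

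### Protocol section 9.2 sets a 7-day and a 15-day reporting deadline in follow-up without relating them, and its serious-event trigger omits death and medically important conditions, which 9.1 counts as serious

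*Protocol*

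**What the plan says.** Section 9.2 treats adverse reactions (AR) and adverse events (AE) in two parallel paragraphs, each with an ordinary rule and a rule for serious cases.

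- **Ordinary rule.** For AEs: "Occurrence and grading of AE are to be documented on the RT-form during the follow-up and sent to the study center within 7 days". The AR paragraph opens in the same way, "Occurrence and grading of AR are to be documented on the forms on acute and chronic toxicity during the follow-up", with the same 7 days.
- **Serious cases.** The trigger for AEs is "In case of an AE causing hospitalization, prolongation of a hospitalization, physical handicap, life threatening events or gametopathy". For these, the duration, the treatment given and a possible causal link "should be documented as SAE and sent to the study center within 24 h during RT and within 15 days during follow-up". The AR paragraph uses the same list and the same two deadlines.

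Section 9.1 draws seriousness more widely. Its examples include "results in death, illness requiring hospitalization, events deemed life-threatening", lasting disability, and "a congenital anomaly/birth defect or medically important condition". Section 9.2.1 classes a fatal outcome as an SAE and refers on to 9.2.3, where no reporting deadline is given.

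One further deadline could bear on a death. Section 9.2.2.1 requires notice within 2 working days of radiotherapy changes that make a patient a dropout. Its dropout entry points to 9.2.3.1, which lists the patient's death.

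**The concern.** A safety reporting scheme should bring serious events to the study center at least as fast as minor ones. During radiotherapy (RT), section 9.2 does this. In follow-up, the only deadline attached to the serious report is longer than the ordinary one, and no text explains why. Two sites could read the section differently and both be compliant.

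The trigger list raises a second, separate question: a site that works from 9.2 alone would not find death or a medically important condition on it.

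The protocol's own oversight depends on these reports. Safety is part of the primary objective (3.1.1). Under 9.2.3.2, an excess of high-grade toxicity, grade V in particular, may end the trial, and the lead investigators must bring this to the ILROG Steering Committee. The Data Monitoring Committee is planned to meet once, after the first year, or when the investigators see a need (9.3). Between meetings, detection rests on what sites send and when. Section 9.2 also states that there is no statutory duty to report SAEs, so the protocol's wording is the only deadline this document gives a site.

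**Working it through.** There is no plan figure to reproduce. The check sets the rules side by side.

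| Event | During RT | During follow-up |
|---|---|---|
| Any AR/AE: occurrence and grade (9.2) | 7 days, if the rule extends to RT | 7 days |
| AR/AE on the 9.2 trigger list: duration, therapy, causal link | 24 h | 15 days |
| Death or medically important condition with no listed feature | 7 days, if the rule extends to RT; for a death perhaps 2 working days (9.2.2.1/9.2.3.1) | 7 days |

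**Deadlines in follow-up**

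1. Difference: 15 − 7 = 8 days. Ratio: 15 / 7 = 2.1.
2. Reading A: the serious rule replaces the ordinary one. A serious late event may then be sent up to 8 days after the date by which a trivial one is due.
3. Reading B: both rules bind. The 7-day sentence covers occurrence and grade and exempts no serious event; the 15-day sentence adds the details. First notice is then due at 7 days for serious and trivial events alike, and the causal information is due 8 days after the grade.
4. Both readings assume that the two clocks start on the same day. Section 9.2 does not say what starts either.

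**Trigger list against definition**

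1. Section 9.1 names six categories: death, hospitalization, threat to life, disability, congenital anomaly, medically important condition.
2. The 9.2 list covers hospitalization (including its prolongation), handicap, threat to life and, through gametopathy, roughly the congenital category. That is four of six.
3. Missing from both the AR and the AE list: death and medically important condition, 6 − 4 = 2.
4. An event outside the list falls back to the ordinary rule. In follow-up that means 7 days, which is shorter than 15, so the omission does not lengthen the deadline there. During RT it means 7 days instead of 24 h, that is 7 − 1 = 6 days longer.
5. Step 4 assumes that the 7-day rule reaches the RT period. Its sentence mentions only follow-up, although it names the RT form. If it does not reach RT, an unlisted event during RT has no deadline in 9.2.

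**The case against.** The best defence is Reading B. The two sentences ask for different content, and nothing releases a site from the 7-day rule when an event is serious. A reader might infer that serious late harm is the slowest to be reported, or that a patient could begin and finish a two-week course before the center hears of an event elsewhere. Both need Reading A, and the text does not establish it. This part of the objection stands. It leaves two points open: no sentence links the two deadlines, and even on Reading B a life-threatening event after RT gets no faster first notice than a mild one.

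A reader might also infer that leaving out death delays the reporting of late deaths. It does not, because the fallback in follow-up is the shorter deadline.

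Deaths are partly covered elsewhere. Section 9.2.1 calls them SAEs, the dropout notice may catch one during RT, and many would follow a listed hospitalization or threat to life. That narrows the gap without closing it. A sudden death need not have a listed feature, and the dropout notice stands under changes in radiotherapy and does not clearly reach follow-up.

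Finally, the consequence is limited. The Steering Committee has a month to decide, 9.2.3.2 sets no numerical boundary that 8 days would cross, and toxicity is still collected at visits up to 2 years. This also stands, and it bears on priority.

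**Conclusion.** The concern holds as two separate contradictions in stated rules.

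- **Deadlines.** In follow-up the serious report is due at 15 days and the ordinary one at 7. Depending on the reading, a serious late event may be reported up to 8 days later than a trivial one, or it gets equal first notice with causal information due 8 days after the grade. The text does not decide between these.
- **Trigger list.** Two of the six seriousness categories in 9.1 are absent from both paragraphs of 9.2. This matters mainly during RT: 7 days against 24 h, if the ordinary rule applies there and the dropout notice does not.

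The sponsor should fix this, but it is not critical to the trial's main result. The response endpoint, its test and the sample size are untouched. It would be tempting to size the harm by the share of calendar time under the 24-hour rule, or by the number of patients enrolled in 15 days. Neither measures harm: the protocol gives no expected rate of serious events, and RT may begin up to 3 months after enrolment.

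**What to change.** Reconcile sections 9.1, 9.2, 9.2.1 and 9.2.2.1/9.2.3.1 in one short amendment:

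1. Use the 9.1 definition of seriousness as the trigger in both the AR and the AE paragraph, so that death and medically important conditions are included.
2. State how the 7-day and 15-day rules relate, for example whether the second is a supplementary report, and whether the 7-day rule also applies during RT.
3. State what starts each clock.
4. Ensure that first notice of a serious AR or AE in follow-up is never due later than that of a non-serious one.
5. Say which deadline governs a death in each phase, and whether the dropout notice is meant to cover it.

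The length of the deadline is for the sponsor to set. The cost is the amendment and a letter to sites, plus somewhat faster paperwork for the few serious events after RT. No treatment rule and no analysis changes.
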